1.2.2.3 Pharmacodynamics

In NHL patients, administration of rituximab resulted in depletion of circulating and tissue-based B cells. Among 166 patients in Study 1, circulating CD19-positive B cells were depleted within the first 3 weeks with sustained depletion for up to 6 to 9 months post treatment in 83% of patients. B-cell recovery began at approximately 6 months and median

B-cell levels returned to normal by 12 months following completion of treatment. There were sustained and statistically significant reductions in both IgM and IgG serum levels observed from 5 through 11 months following rituximab administration; 14% of patients had IgM and/or IgG serum levels below the normal range.

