1.2.2.4 Pharmacokinetics

PKs were characterized in 203 NHL patients receiving 375 mg/m² rituximab weekly by IV infusion for 4 doses. Rituximab was detectable in the serum of patients 3 to 6 months after completion of treatment. The PK profile of rituximab when administered as 6 infusions of 375 mg/m² in combination with 6 cycles of CHOP chemotherapy was similar to that seen with rituximab alone. Based on a population PK analysis of data from 298 NHL patients who received rituximab once weekly or once every three weeks, the estimated median terminal elimination half-life was 22 days (range, 6.1 to 52 days). Patients with higher CD19-positive cell counts or larger measurable tumor lesions at pretreatment had a higher clearance. However, dose adjustment for pretreatment CD19 count or size of tumor lesion is not necessary. Age and gender had no effect on the PK of rituximab. PKs were characterized in 21 patients with CLL receiving rituximab according to the recommended dose and schedule. The estimated median terminal half-life of rituximab was 32 days (range, 14 to 62 days).

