In addition, patients with abnormal renal function may be included if the abnormal function is due to allograft dysfunction resulting from diagnosis of PTLD, or from reduction/cessation of immunosuppression aimed at treatment of PTLD.

3.1.7 Women of child-bearing potential and men must agree to use adequate contraception (hormonal or barrier method of birth control; abstinence) prior to study entry, for the duration of study participation, and for 90 days following completion of therapy. Should a woman become pregnant or suspect she is pregnant while participating in this study, she should inform her treating physician immediately.

3.1.9.1 A female of child-bearing potential is any woman (regardless of sexual orientation, having undergone a tubal ligation, or remaining celibate by choice) who meets the following criteria:

- Has not undergone a hysterectomy or bilateral oophorectomy; or
- Has not been naturally postmenopausal for at least 12 consecutive months (i.e., has had menses at any time in the preceding 12 consecutive months).

3.1.8 Patients must be free of any prior malignancies for ≥ 1 year.
*NOTE: The exception to this would be currently treated squamous cell and basal cell carcinoma of the skin, carcinoma *in situ* of the cervix, breast, or bladder, or surgically removed melanoma *in situ* of the skin (stage 0) with histologically confirmed free margins of excision. In addition, it is well-recognized that patients at highest risk for EBV-related lymphoma (ie, those with chronic immunosuppression) are also at high risk for various malignancies, both invasive and non-invasive. Therefore, exceptions may also be granted on a case-by-case basis, at the discretion of the PI with approval from the Data Monitoring Committee, for those patients with good clinical control of active malignancy, if the EBV-related lymphoma is considered to be a more immediate threat to the subject's health and/or life.*

3.1.9 Patients must have the ability to understand and the willingness to sign a written informed consent. All patients must have signed, witnessed informed consent prior to registration.

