Patients achieving **PD** at first re-staging should be taken off treatment and treated with R-CHOP or similar chemotherapy at the discretion of the local treating investigator.

Patients achieving **SD** should likewise be taken off treatment and treated as above. However, at the discretion of the treating investigator, such patients may receive an additional treatment of the same termed "**Consolidation**".

Consolidation treatment is identical to Induction. If, after Consolidation treatment, these patients achieve CR or PR, they should proceed to Maintenance (see below for description). If, however, these patients are still SD or have progressed to PD, they should be taken off treatment and treated with R-CHOP or similar chemotherapy at the discretion of the local treating investigator.

Patients achieving **CR** or **PR** after the Induction course may receive an additional treatment of the same termed "**Consolidation**". Consolidation treatment is identical to Induction. For patients achieving CR after Induction, in whom avoidance of maintenance therapy is sought, Consolidation may be given as their final planned therapy. Patients who achieve CR after Induction may proceed directly to Maintenance therapy at the discretion of the treating investigator (for instance, if they are not likely to tolerate Consolidation therapy given the toxicity they experienced during Induction).

Following Consolidation, patients will proceed to **Maintenance:** 1.8 mg/kg IV infusion over 30 minutes once every 3 weeks (1 cycle = 3 weeks), for one year from starting induction or until progression of disease. At the discretion of the treating investigator, patients may discontinue brentuximab vedotin after 10 maintenance doses.

4.1.4 **Dose escalation on a per-patient basis (for both Phase I and Phase II):**

For any patient treated with a brentuximab vedotin dose of 0.8 mg/kg for 2 or more 21-day cycles without DLT, subsequent doses can be increased to 1.2 mg/kg, **but only at the discretion of the treating investigator.** *NOTE: the*

basis for escalation, or lack thereof, should be clearly documented in the Treatment eCRF.

4.1.5 Recommended treatment off study in the event of progressive disease or loss of response:

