Clinical suspicion of progressive disease (PD) or loss of response should be investigated radiographically, and if confirmed, will result in removal from active therapy (though any such patient will remain in study follow up; see 4.5, Duration of Therapy). In this case, it is strongly recommended that investigators consider early initiation R-CHOP or similar chemoimmunotherapy (off trial).

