4.7 Duration of Follow Up

Once patients are off treatment (whether treatment is completed or they are withdrawn for any reason) patients will be followed with at least one clinic visit every three months, for up to one year from discontinuation of treatment, then every six months up to 3 years from discontinuation of treatment, or until death, whichever occurs first. Patients removed from treatment for unacceptable adverse events will be followed until resolution or stabilization of the adverse event.

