4.8 Removal of Subjects from Treatment and/or Study

Patients can be removed from the study treatment and/or study at any time at their own request, or they may be withdrawn at the discretion of the investigator for safety, behavioral, or administrative reasons. The reason(s) for discontinuation must be documented and may include:

- 5.5.1 Patient voluntarily withdraws from treatment (follow-up permitted);
- 5.5.2 Patient withdraws consent (termination of treatment and follow-up);
- 5.5.3 Patient is unable to comply with protocol requirements;
- 5.5.4 Patient demonstrates disease progression (unless continued treatment with study drug is deemed appropriate at the discretion of the investigator);
- 5.5.5 Patient experiences toxicity that makes continuation in the protocol unsafe;
- 5.5.6 Treating physician judges continuation on the study would not be in the patient's best interest;
- 5.5.7 Patient becomes pregnant (pregnancy to be reported along same timelines as a serious adverse event);
- 5.5.8 Development of second malignancy (except for basal cell carcinoma or squamous cell carcinoma of the skin) that requires treatment, which would interfere with this study;
- 5.5.9 Patient is lost to follow-up. If a research subject cannot be located to document survival during the follow-up period (up to 3 year after starting study treatment), the subject may be considered "lost to follow-up." All attempts to contact the subject during the follow-up period must be documented and approved by the Data Monitoring Committee.

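### Where the 90-day clause in 3.1.7 is the limit, contraception can end at the short end of the protocol's own 3-to-6-month rituximab detectability window; a 6-month minimum is a cheap fix.

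*Combined protocol and SAP*

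**What the plan says.** **The rule.** Section 3.1.7 covers women of child-bearing potential and men. It requires adequate contraception before entry, and then "for the duration of study participation, and for 90 days following completion of therapy". The two limbs are cumulative, so the longer one governs. Neither 3.1.7 nor any other section defines study participation, and no section gives a reason for 90 days.

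**Follow-up.** Section 4.7 has patients who stop treatment for any reason seen every three months "for up to one year from discontinuation of treatment, then every six months up to 3 years from discontinuation of treatment". Section 4.1.5, on progression or loss of response, says "any such patient will remain in study follow up". Section 4.8 separates stopping treatment (follow-up may continue) from withdrawing consent (both end). It also allows investigator withdrawal from the study and recognises loss to follow-up. Section 4.3 and its Table 4 speak of removal from the study or the trial for toxicity.

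**Rituximab persistence.** Section 1.2.2.4 describes patients given four weekly doses and reports: "Rituximab was detectable in the serum of patients 3 to 6 months after completion of treatment". It gives a median half-life in NHL of 22 days, range 6.1 to 52. Section 1.2.2.3 reports B-cell "sustained depletion for up to 6 to 9 months post treatment in 83% of patients".

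**Last drug given.** Under 4.1.3, for a patient in CR who wishes to avoid maintenance, "Consolidation may be given as their final planned therapy". The same section lets brentuximab vedotin stop after 10 maintenance doses, while 4.1.1.2 schedules rituximab to one year from the first induction dose.

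**The concern.** A contraception rule should have one clear end date, and that date should be reconciled with the drug persistence that the protocol itself reports. Ninety days fits brentuximab vedotin comfortably. For rituximab it falls where the reported detectability window begins, and the protocol does not discuss the difference.

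The undefined term adds to this. If participation includes follow-up of up to 3 years, the 90 days adds nothing for anyone who stays in follow-up. A site that wants the clause to have a purpose could therefore reasonably read participation as treatment only. On that reading 90 days is the limit for every patient at that site. On the other reading it is still the limit for patients who leave the study when therapy ends or soon after.

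What is at stake is patient safety: release from contraception while the protocol's own data say rituximab may still be in serum. Sample size, error rates and power are not affected.

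**Working it through.** There is no planned figure to reproduce. The check compares the 90 days with the protocol's own pharmacology.

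**1. Units.** One month = 365.25/12 = 30.44 days, so 90 days = 2.96 months. Three months is 91.3 days and six months is 182.6 days. Ninety days therefore stops 1.3 days before the start of the window and 92.6 days before its end.

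**2. Rituximab remaining.** Assume single-phase decay, counted from the last dose, as a share of the level at the start of the terminal phase: share = 2^(−t / half-life). The half-lives are from 1.2.2.4.

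| Days since last rituximab | 6.1 d (shortest) | 22 d (median) | 52 d (longest) |
|---|---|---|---|
| 90 | 0.004% (14.8 half-lives) | 5.9% (4.1) | 30% (1.7) |
| 111 | 0.0003% (18.2) | 3.0% (5.0) | 23% (2.1) |
| 182.6 | negligible (29.9) | 0.3% (8.3) | 8.8% (3.5) |

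The 111-day row is for therapy that ends on a brentuximab-only maintenance cycle, 21 days after the last rituximab: 90 + 21 = 111. That is still inside the 3-to-6-month window.

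**3. Brentuximab vedotin.** Section 1.2.1.5 gives a half-life of 4 to 6 days. 90/6 = 15 and 90/4 = 22.5 half-lives, so at most about 0.003% remains. This drug is not the issue.

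**4. Can rituximab be last?** Yes, by two routes.
- Final consolidation: rituximab is given in weeks 1 to 4 and brentuximab vedotin in weeks 1 to 3 only, so the last infusion is rituximab.
- Brentuximab vedotin stopped after 10 maintenance doses: ten doses at 3-week spacing span 9 × 3 = 27 weeks from the start of maintenance. Induction rituximab falls at weeks 0 to 3. Consolidation starts 1 to 3 weeks later (weeks 4 to 6) and its fourth dose is 3 weeks after that (weeks 7 to 9). Maintenance starts a further 1 to 3 weeks on (weeks 8 to 12). The tenth brentuximab dose then falls at about weeks 35 to 39, and rituximab may continue every 6 weeks to week 52.

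**5. Who is limited to 90 days?**

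| Situation | Participation includes follow-up | Participation means treatment only |
|---|---|---|
| Stays in follow-up | Covered while followed, up to 3 years | 90 days |
| Withdraws consent at end of therapy (4.8) | 90 days | 90 days |
| Lost to follow-up, or removed from the study rather than from treatment alone, at or soon after end of therapy | 90 days, unless 4.7 keeps the patient in follow-up | 90 days |

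**The case against.** **Most patients may be covered.** Section 4.7 follows patients who come off treatment for any reason, 4.1.5 calls this study follow-up, and 4.8 distinguishes leaving treatment from leaving the study. On that reading the 90 days is only a minimum for early leavers, and nothing shows that a site read it otherwise. This stands. A reader might infer that every patient is released at 90 days, and the documents do not support that. It would be equally wrong to confine the gap to consent withdrawal and site misreading: loss to follow-up and removal from the study are also in 4.3 and 4.8, although 4.7 appears to keep many withdrawn patients in follow-up.

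**Six months is not a documented safety threshold.** This also stands. The documents give no fetal-risk threshold, no assay limit, and no statement that detectability decides when contraception may end. The window was observed after four weekly doses, while this trial allows eight weekly doses plus maintenance, and 8.8% remains at six months at the longest half-life. B-cell depletion describes the patient's own cells, not drug exposure. Nor do the documents give a specific basis for concern about rituximab exposure in men, whom 3.1.7 also covers.

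**Little is gained.** After consent withdrawal a longer period is only advice. The number affected, of at most 33 patients, is unknown and may be small; patients with progression, and many with stable disease, are directed to further chemotherapy outside the protocol. Consent wording is not visible and may already be longer. These points limit the size of the benefit, but none of them explains the choice of 90 days.

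**Conclusion.** The point holds as a cheap patient-safety improvement. Where the 90-day clause governs, contraception can end at the lower end of the protocol's own rituximab detectability window. About 6% of the terminal-phase level then remains at the median half-life and about 30% at the longest; if the last rituximab was 21 days before the end of therapy, the figures are about 3% and 23%. The 52-day half-life is the extreme of the stated range, not a typical patient, and at the shortest half-life almost nothing remains.

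This rests on single-phase decay and on the half-lives in 1.2.2.4 applying to this population. A reader might infer that fetal harm has been shown or that six months is proven adequate. The documents support neither. They show possible residual exposure and do not explain 90 days against it. The undefined term alone would be a matter of missing detail; the stated 90-day limit is what makes a change worthwhile.

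**What to change.** In 3.1.7, keep the requirement for the whole of study participation. Replace the 90-day clause with: *for at least 6 months after the last dose of rituximab or brentuximab vedotin, whichever is later, even if the patient leaves the study earlier*. This shortens no one's coverage, works under either reading of participation, and starts the clock at a recorded dose date. Stating whether participation includes follow-up would settle the remaining ambiguity, but the minimum does not depend on it.

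Six months is the upper end of the window in 1.2.2.4. The safety team should confirm it or lengthen it, given the longer rituximab exposure here, and should say whether the same interval is needed for men. Match the consent wording.

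Cost: about three more months of contraception for affected patients, and a routine protocol and consent amendment that needs IRB approval before use (11.7). No visit or test is added. After consent withdrawal the period is advice that the study cannot check.

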3.2 Exclusion Criteria

3.2.1 Patients who have received prior treatment for lymphoma are not eligible.

NOTE: Patients may have received corticosteroids for lymphoma for 10 or fewer days at any dose (no washout period required).

NOTE: Patients may have received up to 1 prior dose of rituximab before registration. In this case, patients will only receive 3 doses of rituximab on study, as specified in section 4 1.1.2.1.

3.2.2 Patients who have received chemotherapy (including monoclonal antibodies) or radiotherapy, administered for any condition, within 4 weeks prior to registration are not eligible.

NOTE: Patients may have received one dose of rituximab prior to enrollment. In such cases, patients will only continue with 3 doses of rituximab during induction (4 total doses).

3.2.3 Patients who have had prior surgical intervention for lymphoma, unless performed for the sake of tissue diagnosis or on an urgent basis for disease-related threat to life, limb, or organ function, are not eligible.

3.2.4 Patients with incomplete recovery from adverse events due to agents administered more than 4 weeks prior to registration are not eligible.

3.2.5 Patients must not have ongoing treatment with any other investigational agents ≤ 14 days prior to registration.

3.2.6 Patients must not have known CNS involvement of lymphoma.

3.2.7 Patients must not have a history of allergic reactions attributed to compounds of similar chemical or biologic composition to brentuximab vedotin and/or rituximab.

3.2.8 Patients must not have an uncontrolled intercurrent illness including, but not limited to, ongoing or active infection, symptomatic congestive heart failure, unstable angina pectoris, cardiac arrhythmia, or psychiatric illness/social situations that would limit compliance with study requirements.

3.2.9 Patients must not have known HIV infection.

3.2.10 Patients must not have known JC virus infection and/or progressive multifocal leukoencephalopathy (PML).

3.2.11 Patients are not eligible who have clinically active hepatitis B (tested at screening) or known hepatitis A or C infections.

NOTE: Patients with chronic HCV or HBV infection may enroll if other laboratory criteria are met. Those with HBV surface antigen positivity may enroll only if maintained on appropriate suppressive antiviral therapy, per treating investigator's discretion, for the duration of enrollment in the trial.

3.2.12 Pregnancy or active nursing of an infant is not permitted.

3.2.13 Patients with a prior history of documented pancreatitis are not eligible.

3.2.14 Patients with severe renal impairment (CrCL <30 mL/min) are not eligible. A calculated CrCl is acceptable.

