1.2.2 Rituximab

1.2.2.1 Toxicity Summary

The following serious adverse reactions were observed in patients treated with Rituximab, when used either alone or with other agents:

- Infusion reactions
- Tumor lysis syndrome
- Mucocutaneous reactions
- Progressive multifocal leukoencephalopathy
- Hepatitis B reactivation with fulminant hepatitis
- Infections
- Cardiac arrhythmias
- Renal toxicity
- Bowel obstruction and perforation

The most common adverse reactions of rituximab (incidence $\geq 25\%$) observed in clinical trials of patients with NHL were infusion reactions, fever, lymphopenia, chills, infection, and asthenia. The most common adverse reactions of rituximab (incidence $\geq 25\%$) observed in clinical trials of patients with CLL were: infusion reactions and neutropenia. Because clinical trials are conducted under widely varying conditions, adverse reaction rates observed in the clinical trials of a drug cannot be directly compared to rates in the clinical trials of another drug and may not reflect the rates observed in clinical practice.

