50,000-74,000/ μL	
-1st Occurrence: Notify treating investigator. Withhold current dose until ANC $\geq 1,500/\mu\text{L}$ and platelets $\geq 100,000/\mu\text{L}$. Do not replace missed doses. Restart next treatment at 50% previous dose.
 
-2nd Occurrence: Withhold current dose until ANC $\geq 1,500/\mu\text{L}$ and platelets $\geq 100,000/\mu\text{L}$. Do not replace missed doses. Restart next treatment at 25% previous dose.
 
-3rd Occurrence: Discontinue protocol therapy.

<50,000/ μL	
-1st Occurrence: Withhold current dose until ANC $\geq 1,500/\mu\text{L}$ and platelets $\geq 100,000/\mu\text{L}$. Restart next treatment at 25% previous dose.
 
-2nd Occurrence: Discontinue protocol therapy.

TABLE 4 Drug-Related Non-Hematological Toxicity Dose Reductions for Brentuximab vedotin & Rituximab ¹

CTCAE v 4.03 Grade	Brentuximab vedotin	Rituximab
0-2	No change from original starting dose	No change from original starting dose
3-4	Skip treatment until resolved to \leq Grade 2, then reduce by 33%	May continue if toxicity is clinically attributed to brentuximab vedotin. Otherwise, skip treatment until resolved to \leq Grade 2, then resume at same dose
Second episode of grade 3 or 4 toxicity	Skip treatment until resolved to \leq Grade 2, then reduce by 33%	May continue if toxicity is clinically attributed to brentuximab vedotin. Otherwise, skip treatment until resolved to \leq Grade 2, then resume at same dose
Third episode of grade 3 or 4 toxicity	Remove subject from trial	Remove subject from trial

¹ This table should be followed for all non-hematological toxicities EXCEPT peripheral neuropathy, hyperamylasemia, and pancreatitis, which should be managed as outlined below. In cases involving hyperbilirubinemia that is primarily indirect, and considered not reflective of underlying liver disease (ie, resulting from transfusion of red blood cells), treating investigators may consider avoiding protocol-specified dose reductions, after consultation with principal investigator.

Management of peripheral neuropathy:

- For new or worsening Grade 2 or 3 peripheral neuropathy, brentuximab vedotin should be withheld until neuropathy improves to Grade 1 or baseline and then restarted at a dose of 1.2 mg/kg. Missed doses will not be made up.
- For grade 4 peripheral neuropathy, discontinue treatment with brentuximab vedotin.

Dose modifications regarding hyperamylasemia and pancreatitis

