4.4.2 Allowed concomitant medications

- 4.4.2.1 Solumedrol 125 mg IV over 15 minutes as needed for infusion reactions.
- 4.4.2.2 Symptomatic treatment as needed for nausea, vomiting, and/or diarrhea, including 5-HT3 antagonists, corticosteroids, benzodiazepines, and anti-motility agents.
- 4.4.2.3 Topical and systemic treatment for rash, including corticosteroids.
- 4.4.2.4 Hormonal birth control medications.
- 4.4.2.5 Concurrent antiviral therapy for HBV surface antigen positivity.
- 4.4.2.6 G-CSF (Filgrastim), including Neulasta®, may be added for low ANC while any requisite dose reduction in study agent is instituted, at treating physician's discretion.

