⁶Phase II patients only: One red top tube and one green top tube will be drawn at baseline OR day 1 of induction, and day 1 of the first 3 maintenance cycles. Blood products will be frozen and stored in the Pathology Core Facility for future, unspecified use.

⁷ Brentuximab vedotin will be given intravenously over approximately 30 minutes at the specified time points. The dose will be 1.2mg/kg during induction and optional consolidation (see section 4.1) and 1.8mg/kg during maintenance. Lab values for CBC and Chemistry panels must be resulted prior to dosing to assess for dose delays or modifications.

Consolidation treatment should start 7-21 days after the fourth induction dose of rituximab. Maintenance treatment should start 7-21 days after the fourth consolidation dose of rituximab.

⁸ Rituximab will be given intravenously at a dose of 375mg/m² at the specified time points. Rituximab should be given immediately before brentuximab vedotin on days when both drugs are administered. See section 4.1 for more details. Lab values for CBC and Chemistry panels must be resulted prior to dosing to assess for dose delays or modifications.⁹ Hepatitis testing at screening will include HepBsAg and HepBcAb within 4 months prior to registration. ¹⁰ The End of Treatment visit should take place 21-28 days after the patient's last dose of study drug.

¹¹ Patients will be followed every three months for one year following discontinuation of study treatment, then every six months for a total of three years following discontinuation of study treatment, or until death, whichever comes first.

¹² Consolidation treatment is optional for patients who achieve response (PR or CR; see section 4.1.3 regarding SD) after induction. In addition, any patients achieving CR to induction, in whom avoidance of Maintenance therapy is sought, can receive consolidation as their final planned therapy.

¹³ Treatment and assessments will take place on Day 1 of each Week

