3.1.3, 3.1.4 (Inclusion Criteria); 3.2.1 (Exclusion criteria)	Requirements to have no prior treatment or surgical intervention included as inclusion criteria	Removed from inclusion and included as exclusion criteria 3.2.1 and 3.2.3.	More appropriate as exclusion criteria
3.2.1 (Exclusion Criteria)	Excluded patients with no history of immunosuppression or EBV-related DLBCL	Removes exclusion criteria	Redundant of inclusion 3.1.1, which states that lymphoproliferative disease must be immunosuppressed
3.2.2, 3.2.1 (Exclusion Criteria); 4.1.1.2.1 (Pre-Registration Rituximab)	n/a	Patients are allowed to receive one dose of rituximab prior to entering the study, and in such cases, patients will only have 3 doses during induction (a total of 4 doses)	Added for clarification and consistency
3.2.4, 3.2.5 (Exclusion Criteria); 4.4.3 (Concomitant medications and treatments not allowed)	n/a	Clarifies timing of washout as 4 weeks or 14 days prior to registration for unrecovered AE's, chemotherapy, radiotherapy or investigational agents, respectively	Clarification
3.2.11 (Exclusion Criteria); 5.0 (Study Procedures)	Patients were not eligible with clinically active Hep A, B, or C	Clarifies that Hep B will be tested at screening, and Hep A and C will be based on known history. Adds Hepatitis B testing within 4 months prior to registration.	Hepatitis B testing is standard prior to rituximab treatment.
4.0 (Treatment Plan)	n/a	Adds paragraph and table as a treatment summary	Added for clarity and simplification

		before subsequent details of dosage and administration (updates all subsequent table numbers and references)	
4.1.1 (Phase I and II dosage); 4.1.3 (Phase II Treatment)	Referred to Phase I dosing only	Refers to both Phase I and II dosing details with a statement that RP2D was found to be the same as Phase I dosing on 3/12/2014. Refers to section 4.1.3 for Phase II instructions for treatment after SD	Updated for accuracy and simplicity
4.1.6 (Administration Details, Table 2)	Rituximab treatment for the full study was listed in a shaded box	Separates rituximab treatment by induction/consolidation vs maintenance, similar to BV	Revised for clarity
4.2 (DLT and MTD)	n/a	Adds "For Phase I..." to preface DLT definitions	Clarification
4.3 (Toxicities and Dosing Delays/Dose Modifications)	Referenced section 1.3.1.1 for risk information	Updates to section 1.2.2.1	Revised for accuracy

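### HBcAb is tested at screening but a positive result triggers no rule, and Table 4 allows more rituximab after a liver event without an HBV test

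*Combined protocol and SAP*

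**What the plan says.** **Screening.** Table 5 footnote 9: "Hepatitis testing at screening will include HepBsAg and HepBcAb within 4 months prior to registration". The hepatitis B row of Table 5 is marked in the baseline column only. Appendix C gives the reason for adding the test under Amendment 8: "Hepatitis B testing is standard prior to rituximab treatment".

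**Entry.** Section 3.2.11 excludes clinically active hepatitis B. Its NOTE admits chronic HBV infection if the other laboratory criteria are met and adds: "Those with HBV surface antigen positivity may enroll only if maintained on appropriate suppressive antiviral therapy". The matching entry under allowed medications, 4.4.2.5, reads: "Concurrent antiviral therapy for HBV surface antigen positivity". Neither mentions HBcAb.

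**Known risk.** Among the serious reactions to rituximab, section 1.2.2.1 lists "Hepatitis B reactivation with fulminant hepatitis".

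**Dosing after toxicity.** Table 4 covers drug-related non-hematological toxicity. Footnote 1: "This table should be followed for all non-hematological toxicities EXCEPT peripheral neuropathy, hyperamylasemia, and pancreatitis". At Grade 0-2, the entry for both agents is "No change from original starting dose". At a first or second Grade 3-4 episode, the rituximab entry begins: "May continue if toxicity is clinically attributed to brentuximab vedotin". Otherwise rituximab is skipped until the event is Grade 2 or lower and then given again at the same dose. A third episode removes the patient.

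**The concern.** The protocol collects a result and then does not use it. It names HBV reactivation as a serious rituximab reaction and tests two markers before rituximab, but writes a management rule for only one of them. The patient who falls between the two is the one with HBcAb positive and HBsAg negative.

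The dosing rules add to this. The chemistry panel can show liver injury but not its cause. Section 8.1.10 lists hepatotoxicity for brentuximab vedotin, so a liver event on the combination has a ready alternative explanation. Where both agents could be responsible, section 4.3 tells the investigator to modify the likelier agent first, and to adjust brentuximab vedotin before rituximab. An investigator who follows the written rules could therefore give rituximab during or just after an HBV reactivation without having looked for it. What is at stake is patient safety; no estimate or test in the trial changes.

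**Working it through.** The plan gives no figure on this point, so the check sets the provisions side by side.

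**1. What each screening result leads to**

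| HBsAg | HBcAb | Entry (if not clinically active) | Antiviral required | HBV test after screening |
|---|---|---|---|---|
| positive | either | allowed with antiviral | yes (3.2.11 NOTE) | none scheduled |
| negative | positive | not excluded | none stated | none scheduled |
| negative | negative | allowed | none needed | none scheduled |

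Clinically active is not defined in 3.2.11, but nothing there makes an HBcAb result alone a bar to entry.

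**2. What happens when a liver event occurs**

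- *Judged drug-related, Grade 0-2:* rituximab is unchanged.
- *Judged drug-related, Grade 3-4, attributed to brentuximab vedotin:* rituximab may continue; brentuximab vedotin is skipped, then reduced by 33%.
- *Judged drug-related, Grade 3-4, not so attributed:* rituximab is skipped, then resumed at the same dose once at Grade 2 or lower.
- *Judged unrelated:* Table 4 does not apply, and no other section holds rituximab for HBV.

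No branch requires an HBV test. Of the three exceptions in footnote 1, none concerns HBV.

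**3. How far the removal rule limits this.** Section 4.3 removes a patient who misses more than 3 consecutive administrations for toxicity. Assume that these are brentuximab vedotin doses. In maintenance that drug is given every cycle and rituximab on even cycles. Three consecutive cycles contain two even ones if the run starts on an even cycle (2, 3, 4) and one if it starts on an odd cycle (3, 4, 5). So 1 or 2 full-dose rituximab infusions could be given while brentuximab vedotin is withheld, before the fourth missed dose forces removal. This shows how the rule operates; it does not measure the risk.

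**4. After treatment.** Table 5 marks chemistries through maintenance, but not in the off-treatment or follow-up columns. History and physical examination are scheduled in both. Section 1.2.2.3 puts return of median B-cell levels to normal at 12 months after rituximab.

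**5. Cost of one possible monitoring schedule.** Suppose HBV DNA is tested at baseline, at day 1 of consolidation if given, at each maintenance rituximab dose, and at the quarterly visits of the first follow-up year (12 / 3 = 4). Count the first induction dose as day 1 and treat to day 365. Table 5 footnote 7 gives gaps of 7-21 days between phases; I assume the same gap when consolidation is omitted.

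- *No consolidation:* maintenance starts on day 22 + 7 to 22 + 21, that is day 29-43. The first even cycle is 21 days later, day 50-64, then every 42 days. (365 - 50)/42 = 7.5 and (365 - 64)/42 = 7.2, so 8 doses either way. Tests: 1 + 8 + 4 = 13.
- *With consolidation:* the first maintenance rituximab falls on day 78-106. (365 - 78)/42 = 6.8 and (365 - 106)/42 = 6.2, so 7 doses either way. Tests: 1 + 1 + 7 + 4 = 13.

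**The case against.** The strongest reply is that the documents never say that isolated HBcAb positivity carries the reactivation risk, and give no prevalence or rate. On that view the protocol merely leaves a result to clinical judgment, and a one-line clarification would do. The missing rate is a fair point, and it limits what can be said about size. But the protocol itself chose to require HBcAb before rituximab and named the hazard, and it did not leave HBsAg-positive patients to judgment alone. Section 11.6 also expects the study to be run as written outside emergencies.

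A second reply is that safeguards exist. They do, and they count:

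- Section 4.4.3 does not prohibit antivirals, so a site may give prophylaxis.
- Sections 4.6 and 4.8 allow stopping for intercurrent illness, unacceptable or unsafe toxicity, or investigator judgment.
- Hepatitis that is life-threatening or leads to hospitalization is a serious event under 7.2.3. Under 7.4.1 it is reported within 24 hours to the quality assurance monitor and the manufacturer, and reviewed by the DMC at its next meeting.
- Section 7.1 follows open events, and 11.5 sets high-intensity monitoring.

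None of these requires the test that would identify the cause.

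A reader might infer that the protocol directs rituximab to be given through HBV hepatitis. The documents do not support that. Table 4 applies only to drug-related events, continuation is permissive and depends on clinical attribution, and the instruction to adjust brentuximab vedotin first does not tell anyone to blame it for a viral event. A reader might also infer that 4.4.2.5 bars antivirals for HBcAb-positive patients; it is a list of allowed drugs, and the prohibition list does not include them.

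**Conclusion.** The gap is real and worth closing. An HBsAg-negative, HBcAb-positive patient without clinically active disease may enroll with no required prophylaxis or HBV monitoring. After a drug-related liver event, rituximab may continue or resume at full dose with no HBV test; after an event judged unrelated, no HBV hold rule exists.

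The conclusion assumes that HBcAb was added because a positive result bears on reactivation risk, which is the natural reading of footnote 9 together with the Amendment 8 rationale. It does not establish how often harm would occur: the number of affected patients and their risk are not given, and counts of doses or visits do not stand in for them. Sample size, error rates and endpoints are untouched. This is a change that should be made on safety grounds, not a flaw that invalidates the trial.

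**What to change.** 1. **Section 3.2.11 NOTE.** Add that HBsAg-negative, HBcAb-positive patients may enroll only with antiviral prophylaxis, or with periodic HBV DNA monitoring at existing visits during treatment and the first year of follow-up. The sponsor should set the exact schedule and duration, since the documents dictate neither. Align 4.4.2.5 for consistency, and add a conditional HBV DNA row to Table 5.
2. **Table 4 footnote 1.** Add HBV reactivation to the exceptions. In any HBsAg- or HBcAb-positive patient, test for HBV at a new significant rise in ALT, AST or bilirubin before attributing it or giving more rituximab. If reactivation is confirmed, hold rituximab, start antiviral therapy, and do not resume until HBV is controlled. The protocol already has this pattern: an elevated amylase triggers a lipase test, and pancreatitis has its own hold and stop rules.

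**Cost.** A few lines of wording. For affected patients only, either antiviral drug or conditional blood tests: 13 for a patient completing one year under the illustrative schedule above, fewer if the sponsor chooses a lighter one. Footnote 9 already requires both screening tests, but Amendment 8 introduced that requirement, so any ongoing patient registered before it who lacks an HBcAb result needs a one-time test. No patient who accepts either option loses eligibility. The change helps only patients still to be enrolled, on treatment or in follow-up.
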